#### For PROCESS EVALUATION

We will collect qualitative data from key informants and important stakeholders. As this effort isn't linked to a specific hypothesis and doesn't rely on quantitative analyses, no power analysis is specified to determine sample size.

#### Data Analysis

##### FOR EFFECTIVENESS TRIAL:

Primary Hypotheses (regarding functional and service-related outcomes):

Hypothesis 1 (H1): Compared to those receiving a general medical illness education and support group, participants receiving Living Well will demonstrate greater improved general health functioning including both physical and emotional functioning.

To test the null hypothesis of no difference in improved general health functioning, we will use a longitudinal mixed effects model to compare change in mean physical and emotional health functioning from randomization to post-treatment. Regression equation (random effects not presented) at each time point will be:

SF12 function = Intercept + site + covariates + study condition + time + study-condition\*time + error

Notes: (1) Test of the null hypothesis of no difference in change from randomization to the post-treatment assessment will be conducted using a specified contrast. (2) "Study condition" is a dichotomous variable indicating study condition; (3) A random intercept and random slope (coefficient for time) will also be specified for the model; (4) The "time" variable will be entered as a continuous variable with possible values 0, 3, and 6 corresponding to the three assessment points (randomization, post-treatment, & 3-month follow-up); (5) The "covariates" terms represent adjustment for age, race, gender, and important potential confounders and will include Charlson comorbidity index score, chronic somatic illness

category, and any other covariate found to significantly differ at randomization (provided no significant collinearities are found). We are expecting few chance differences at randomization due to large sample size and random study condition assignment; (6) We have included a “site” term to adjust for site differences.

Hypothesis 2 (H2): Compared to the medical illness education and support group, the Living Well group will have a lower proportion of participants who will have had an emergency room visit for management of a chronic medical condition during the six months after randomization.

For proportion with ER use in the past 6 months, we will use a random intercept mixed effects model since this outcome is assessed at only 2 time points. We will use a model that assumes no difference at randomization given the large sample size and randomization to study condition. Thus we will not include study condition as a main effect which would correspond to an assumption of unequal randomization rate of ER use. Some chance variation is expected and we will test the assumption of equal randomization rates with a chi-square test comparing the ER use rates by study condition. This model is equivalent to adjusting for randomization in the continuous case and we are taking this approach to be able to have .80 power to detect a smaller percentage point difference in ER use (50) at the 3 month follow-up assessment than if we didn’t assume equal rates at randomization. In the very unlikely scenario of a statistical difference at randomization we will add the study condition main effect to the model below, and the test of the null for H2 will continue to be the test that the coefficient for the study-condition-by-time interaction term is zero. To compare the two conditions on probability (p) of an ER visit, we let the outcome variable  $Y = 1$  if the participant had an ER visit in the prior 6 months (at randomization or at 3-month follow-up) and  $Y = 0$  if participant did not have an ER visit. Analysis model (logistic mixed effects model, random intercept not displayed) will be:

$$\text{logit}(E[Y]) = \text{Intercept} + \text{site} + \text{covariates} + \text{time} + \text{study-condition} \cdot \text{time}$$

where  $E[Y] = p = \text{probability participant has an ER visit in the prior six months at either randomization or 3 month follow-up (depending on “time” variable)}$ .

Notes: (1) Test of H2 will be the F-test that the coefficient for the study condition-by-time interaction is zero; (2) Study condition indicator main effect is omitted based on assumption of equal rates at randomization as discussed above; (3) For this hypothesis, “time” is a binary variable indicating assessment at 3 months post-treatment versus assessment at randomization; (4) The “covariates” terms represent adjustment for age, race, gender, Charlson comorbidity index score, chronic somatic illness category and other potential confounders found to be significantly different at randomization, (5) We have included a “site” term to adjust for site differences.

In exploratory analyses we will categorize evident causes for emergency room admission and describe and compare the distribution of causes across the 5 chronic medical condition categories using a two-way table with row percentages. Associations between chronic medical condition and cause of emergency room admission will aid us in interpreting results for our ER primary outcome.

Secondary Hypotheses (3 and 4 - regarding more proximal attitudinal and behavioral outcomes):

Hypothesis 3 (H3): Compared to those receiving a general medical illness education and support group, participants receiving Living Well will report improved health-related self-efficacy and patient activation. Further, such improvements will mediate the effects on functional outcomes and ER use.

For self-efficacy and patient activation as outcomes, we will use a parallel model as for Hypothesis 1 to Version 9, 5/1/2015

compare the two study conditions. To test whether change in health-related self-efficacy or patient activation mediates the effect of Living Well we will estimate the mediated effect with a 95% confidence interval. When there is a mediating variable (i.e. mediator), the total effect of treatment can be divided into two components: (1) the direct effect of treatment (independent of the mediator), and (2) the mediated effect (i.e. indirect effect of treatment through the mediator (50). To estimate the mediated effect we will first estimate the total effect of Living Well and second, the direct effect of Living Well, and then estimate the mediated effect by subtracting the second from first. The estimate of the total effect of Living Well will be the treatment effect from the primary analysis model under either H1 or H2. The estimate of the direct effect of Living Well will be the treatment effect of Living Well after adjusting for the mediator. The mediator will be the change score of health-related self-efficacy or patient activation from randomization to post-treatment (for the functional outcomes) or randomization to the 3 month follow-up (for ER use). For statistical inference we will produce a 95% confidence interval around the mediated effect with a bootstrap procedure (51). We will interpret such a 95% confidence interval excluding zero as a statistically significant mediated effect.

Hypothesis 4 (H4): Compared to those receiving a general medical illness education and support group, participants receiving Living Well will report improved self-management behaviors. Further, such improvements will mediate the effects of the functional and service outcomes specified above.

We will use a parallel model as for Hypothesis 1 to compare the two conditions on the self-management behavior scales at post-treatment. The tests of mediation will be directly parallel to those described for the test of mediation in Hypothesis 3 for the functional and ER use outcome variables.

Secondary Hypothesis 5: Living Well participants will sustain improvements across functional, attitudinal and behavioral outcomes at follow-up (3 months post-treatment).

We will test sustained improvement by testing the null hypothesis of no difference in change from randomization to the 3-month follow-up assessment (2-sided test) which will be the test that the coefficient for the study condition-by-time interaction term in the primary model (see H1) is zero. This hypothesis applies only to outcomes obtained from interview, not for ER visit and other 6-month service utilization variables. All available data will be included in these intent-to-treat analyses. The aforementioned analysis plan regarding dropout will be used.

Exploratory analyses: We will conduct several exploratory analyses.

One, in the Living Well group we will utilize data collected at consent to examine outcome trajectories and change in trajectories in the transition from the pre-intervention period (2 months on average) to the intervention period (randomization to post-tx; 3 months) and the post-intervention period (post-tx to follow-up; 3 months). For this analysis, time will be treated as continuous as time from consent to randomization will vary. A spline will be used starting at randomization to detect change in slope when the intervention commences. This analysis will allow comparison of the Living Well group to themselves prior to intervention. Two, we will examine whether improvements on primary and secondary outcomes in the Living Well condition relative to the control condition differ among 5 chronic medical condition subgroups: a) diabetes; b) a respiratory illnesses (including asthma and COPD); c) arthritis, d) a cardiovascular condition (e.g. congestive heart failure); or e) two or more of (a) thru (d). We will describe treatment effects by chronic illness sub-group, computing average treatment effect for each subgroup. We will also add the 3-way interaction term between study condition, time, and chronic illness category to the primary analysis models in order to perform a global test of differential improvement on outcomes by

chronic medical condition subgroup.

Two, we will examine potential covariate moderators of treatment effect (e.g. participant demographic and clinical characteristics-see list of measures above) on the effectiveness of the intervention. To do this we will utilize the primary models but add the 3-way interaction term between the participant characteristic of interest, study condition indicator and time and through a contrast, test the null hypothesis of no relationship between the covariate and improvement on study outcomes. Three, we will examine effects on additional medical services utilization outcomes (e.g. somatic inpatient hospitalization, outpatient visits) as well as on medication adherence. Models parallel to H2 (ER use) will be used to examine treatment effects on these secondary outcomes. Four, we will examine whether treatment effects differed by site. For these analyses we will include the 3-way interaction term between study condition, time, and site to test overall interaction with an omnibus F-test. If the F-test is significant we will report treatment effects by site, and assess site differences in participant characteristics and otherwise investigate and summarize site characteristics that might explain differences. Five, we will examine how “dose” of intervention (i.e. number of sessions attended) and participation ratings (measured using the Group Performance measure described in the measures section) relate to study outcomes. Separately, in both the Living Well and the control condition we will use regression models to examine whether the covariate (either number of sessions attended or the Group Performance measure) is associated with improvement on outcomes. Models for these analyses (whether outcome is assessed at all 3 time points or just at randomization and 3 mo f/u) will include time and the dose-by-time interaction term to assess the relationship between dose and trajectory over time. For ER use and other dichotomous service utilization outcomes this analysis will assess change in proportion with ER in relation to dose. Six, we will similarly examine how fidelity ratings of adherence and competence relate to the functional, attitudinal, behavioral, and service related outcomes specified. In models similar to those used above to examine dose response relationships we will examine the relationship between overall adherence (and competence) and change in outcomes separately for each condition.

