### **Sample Size**

For EFFECTIVENESS TRIAL:

This Randomized Controlled Effectiveness Trial is powered to detect differences on the two primary outcomes: (1) significantly reduced proportion of participants with an ER visit at the 3-month follow-up assessment (6 months post randomization) in the Living Well condition versus control, (2) significantly improved health functioning at post-treatment in the Living Well condition versus control as measured by the SF-12.

ER Visits. In our prior pilot the proportion with an ER visit in the Living Well condition at the 3-month follow-up was 10.7% and in the control condition it was 27.6%. For this power calculation we assumed that the proportion with an ER visit in the Living Well condition at the 3-month follow-up will be 10.7%. However, since we have an active control in this proposal, we specify a lower percentage in the control condition (versus estimate from the pilot study) equal to 25%, and thus a 14.3 percentage point difference. With a two-tailed, alpha .05 level test, and power = .80 to detect this 14.3 percentage point difference we calculate that we will need n = 250 (125 per condition). The percentage point difference that can be detected could be somewhat higher or lower depending on the inter-correlations among the covariates and ER response variable. As proportion with an ER visit will be obtained from VA electronic medical charts for all randomized participants, loss to follow-up is not a significant concern for this outcome. This calculation is conservative -- we would actually have power equal to .80 to detect a smaller difference because the above calculation is based on a basic z-test of proportions, whereas the analysis model

specified above is more powerful. Calculation was performed using PASS version 11.0 (from NCSS, LLC) software. We acknowledge that use of the ER may be different in the VA context given the co-location of medical and psychiatric care, but as evidenced in our previous work (see section A.3), we found that veterans with SMI used the VA ER for medical care at rates comparable to (even greater than) those in our community sample. Specifically, the rate of use in the VA sample was 43% and the baseline rate in the Living Well sample was 31.3%.

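### Linear time in the H1 model makes the primary post-treatment test identical to H5 and gives the month-3 score almost no weight

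*Protocol*

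**What the plan says.** The Sample Size section defines the primary functional outcome as "significantly improved health functioning at post-treatment in the Living Well condition versus control as measured by the SF-12".

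The Data Analysis section, under Hypothesis 1, gives the model as "SF12 function = Intercept + site + covariates + study condition + time", followed by the condition-by-time product and error. Three of its notes matter here:

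- Note (1): "Test of the null hypothesis of no difference in change from randomization to the post-treatment assessment will be conducted using a specified contrast".
- Note (3): "A random intercept and random slope (coefficient for time) will also be specified for the model".
- Note (4): the time "variable will be entered as a continuous variable with possible values 0, 3, and 6 corresponding to the three assessment points".

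Secondary Hypothesis 5 concerns change from randomization to the follow-up three months after treatment (month 6). Its test is described as one "which will be the test that the coefficient for the study condition-by-time interaction term in the primary model (see H1) is zero".

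Hypotheses 3 and 4 use a model parallel to that of Hypothesis 1. Nothing in the Data Analysis section gives this model visit indicators, a quadratic term or a knot at month 3. The only spline is exploratory, is confined to the Living Well arm, and starts at randomization.

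**The concern.** A straight line has one slope. If the arms can differ over time only through one interaction coefficient, the model has no separate quantity for the effect at month 3. The primary post-treatment contrast and the retention test become rescaled versions of each other, and the estimate is driven by the two end visits.

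Three things are at stake:

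- An effect present at the end of treatment that fades by month 6 would be underestimated and often missed. An effect that appears only at month 6 would be credited to post-treatment.
- The sustained gain that Hypothesis 5 predicts is a plateau, which a line through months 0, 3 and 6 cannot represent. The reported post-treatment effect would be half the true one.
- The primary result and the retention result could never differ, so Hypothesis 5 would add no evidence beyond Hypothesis 1.

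Hypotheses 3 and 4 inherit the problem. The mediation analysis for the functional outcomes does too: it pairs a mediator measured as change to post-treatment with a total effect that is really half the 6-month change.

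**Working it through.** **Inputs from the protocol.** Sample Size: effect 0.40 SD at post-treatment, two-sided alpha 0.05, correlation r = 0.50, 250 randomized (125 per arm), 12% loss by post-treatment leaving 110 per arm, stated power 0.89. Hypothesis 1: visits at 0, 3 and 6 months, linear time, random intercept and slope. **Not given, so assumed:** the month-6 SF-12 effect (range 0 to 0.80 SD) and further losses between months 3 and 6 (0 to 30 per arm).

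**The plan's own power figure.** Power = Φ(d / √(v × 2/n) − 1.96), with v = 2(1 − r) = 1 for a change score and v = 1 − r² = 0.75 for baseline adjustment.

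- Change score, n = 110: 0.40/√(2/110) = 0.40/0.1348 = 2.97, power 0.843.
- Baseline-adjusted, n = 110: 0.40/√(1.5/110) = 0.40/0.1168 = 3.43, power 0.929.
- Change score, n = 125: 0.40/√(2/125) = 3.16, power 0.885.

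The stated 0.89 matches the change score with no attrition and neither of the figures at 110 per arm. The argument below does not depend on this.

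**Step 1: one test.** With a single interaction coefficient b, the between-arm difference in change is 3b to month 3 and 6b to month 6. Estimate and standard error scale together, so 3b/SE(3b) = 6b/SE(6b) = b/SE(b). This is exact, with or without missing data.

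**Step 2: weights.** With complete data under compound symmetry, or a random intercept and slope on the same time variable, the estimated slope weights the visits by (t − 3)/Σ(t − 3)² = (−3, 0, 3)/18 = (−1, 0, 1)/6. Multiplying by 3, the month-3 contrast weights the arm differences at months 0, 3 and 6 by −0.5, 0 and +0.5. Numerical generalized least squares gave the same weights under compound symmetry and two random-slope covariances.

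As a check, mixed models were fitted to one simulated trial. Adding 1.0 SD to every Living Well month-3 score left b at 0.0601. The z statistic moved from 2.36 to 2.15, only through the residual variance. These fits gave convergence warnings, so the conclusion rests on the algebra.

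**Step 3: size with complete data.** With no baseline difference, the reported month-3 effect is half the month-6 effect d6. Its standard error is 0.1348/2 = 0.0674, so z = d6/0.1348. Two-sided power is Φ(z − 1.96) + Φ(−z − 1.96). Figures use compound symmetry, r = 0.50 and 110 per arm.

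| True effect, month 3 | True effect, month 6 | Linear time: reported month-3 effect | Power | Time as factor: month-3 effect | Power |
|---|---|---|---|---|---|
| 0.40 | 0.80 | 0.40 | >0.99 | 0.40 | 0.84 |
| 0.40 | 0.40 | 0.20 | 0.84 | 0.40 | 0.84 |
| 0.40 | 0.20 | 0.10 | 0.32 | 0.40 | 0.84 |
| 0.40 | 0 | 0.00 | 0.05 | 0.40 | 0.84 |
| 0 | 0.40 | 0.20 | 0.84 | 0.00 | 0.05 |

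In the last row, the linear model's 0.84 is the chance of declaring a post-treatment effect that does not exist.

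**Step 4: attrition.** Start from 125 per arm with 15 (12%) lost before month 3. Weight ranges are over the three covariances; estimates and powers are for compound symmetry.

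| Further loss per arm before month 6 | Weight on month 3 | Reported effect when d6 = 0.40 / 0.20 / 0 | Power |
|---|---|---|---|
| 0 | 0.01 | 0.20 / 0.10 / 0.00 | 0.86 / 0.34 / 0.05 |
| 10 | 0.03 to 0.05 | 0.21 / 0.11 / 0.01 | 0.85 / 0.36 / 0.05 |
| 30 | 0.09 to 0.14 | 0.22 / 0.13 / 0.04 | 0.84 / 0.40 / 0.08 |

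**The case against.** The strongest reply is that the power loss depends on an assumption. The protocol gives no month-6 effect. It expects gains to be sustained, and Living Well has monthly booster sessions between months 3 and 6. If the effect is fully sustained, power is 0.84 under either coding. If it doubles by month 6, the linear model has more power and its month-3 estimate is right. This stands: power falls only if the effect fades. It does not answer the halved estimate under a plateau, which is the pattern the protocol predicts.

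Second, with complete data 6b is exactly the arm difference in change from month 0 to month 6, so the contrast for Hypothesis 5 is the intended one. That also stands. The defect lies in Hypothesis 1 and the parallel Hypothesis 3 and 4 comparisons. What Hypothesis 5 loses is independence from them.

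Third, the wording suggests that visit-specific means may have been intended. Note (1) asks for a contrast where a coefficient test would do, and the exploratory spline analysis announces continuous time as if it were a departure. That may be so, but note (4) states linear coding outright, and no contrast in that model can separate month 3 from month 6. Because the coding is stated, it is not a detail left open for a later analysis plan.

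Finally, the month-3 weight is not exactly zero once participants drop out. This is correct, but even with 30 further losses per arm it stays at or below 0.14.

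**Conclusion.** The concern holds. As written, the primary post-treatment test and the Hypothesis 5 test are the same test; this is algebra and needs no assumption about the data. With complete data the month-3 score has zero weight in the month-3 contrast, and with the attrition examined the weight is 0.01 to 0.14.

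The effect on the estimate is large. A true 0.40 SD effect at month 3 is reported as 0.20 if sustained, 0.10 if half faded and 0.00 if fully faded. Power is 0.84, 0.32 and 0.05 respectively, against 0.84 throughout with time as a factor. These figures assume r = 0.50, 110 per arm with complete data, compound symmetry and the month-6 effects shown. The linear model recovers the month-3 effect only if benefit keeps growing at the same rate to month 6, which the protocol does not predict.

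**What to change.** In the Hypothesis 1 model, replace note (4) so that time is a three-level factor (randomization, month 3, month 6) with condition-by-visit terms. Define the Hypothesis 1 test as the between-arm difference in change from randomization to month 3, and the Hypothesis 5 test as the separate contrast to month 6. Reword Hypothesis 5, which now refers to a single interaction coefficient. Carry the change through to Hypotheses 3 and 4 and to the total and direct effects in the mediation analysis.

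A linear spline with a knot at month 3 would serve equally, since with three visits it fits the same means. The random-effects structure should be restated at the same time; an unstructured covariance or a random intercept would do.

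The cost is a wording change and two more fixed-effect coefficients (two time-related terms become four). No extra data, visits or participants are needed. The change should be made before unblinded outcome data are examined.

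### In the H1 model, site and the covariates enter only as main effects, so the stated adjustment corrects SF-12 level but essentially not the condition-by-time contrast that H1 tests

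*Protocol*

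**What the plan says.** The protocol's Data Analysis section prints the H1 equation as "SF12 function = Intercept + site + covariates + study condition + time", followed by the condition-by-time product and error. That product is the only interaction in the model. The notes to H1 then fix the following:

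- Note (1), the test: "Test of the null hypothesis of no difference in change from randomization to the post-treatment assessment will be conducted using a specified contrast".
- Note (3), random effects: "A random intercept and random slope (coefficient for time) will also be specified for the model".
- Note (4), time: the "variable will be entered as a continuous variable with possible values 0, 3, and 6 corresponding to the three assessment points".
- Note (5), covariates: these "terms represent adjustment for age, race, gender, and important potential confounders". They include the Charlson score, the chronic illness category and "any other covariate found to significantly differ at randomization".
- Note (6), site: a term to adjust for differences between sites.

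The same structure is carried to other hypotheses. For H3 the text reads "For self-efficacy and patient activation as outcomes, we will use a parallel model as for Hypothesis 1", H4 likewise uses a parallel model, and H5 tests the condition-by-time coefficient of the H1 model. H2 is built differently: "Study condition indicator main effect is omitted based on assumption of equal rates at randomization".

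**The concern.** Every named covariate, and site, is constant within a person. A main effect of such a variable moves a person's SF-12 level by the same amount at all three assessments. H1 does not test level. It tests change, and any imbalance in level between arms is already absorbed by the free condition main effect. Notes (5) and (6) therefore describe an adjustment that the printed equation does not apply to the quantity being tested.

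The rule for adding covariates that differ at randomization exists to deal with chance imbalance. For the primary SF-12 contrast it deals with essentially none. If comorbidity, illness category or site predicts change and happens to be unbalanced, the estimate carries that imbalance although the model appears to be adjusted for it. Precision from covariates that predict change is also given up.

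**Working it through.** **Inputs.** From the H1 notes: times 0, 3 and 6, random intercept and slope, covariates and site as main effects. From Sample Size: 125 per arm randomized, 110 per arm after 12% loss, correlation .50, planned effect .40 SD. The plan gives no figure for the effect of the adjustment, so there is none to reproduce. Its stated SF-12 power does not enter this check.

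**Step 1: algebra with complete data.** Reduce each person to an intercept a and a slope b. With times 0, 3 and 6, b = (y at 6 − y at 0)/6. The model is then two equations, with T for condition and x for site and covariates:

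- a = α0 + α1·T + α2·x + u
- b = β0 + β1·T + v

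The H1 contrast is 3·β1. A term in x that is constant over visits cancels from b. The errors u and v are correlated, but the slope equation's regressors are a subset of the intercept equation's. The distribution of a given b has its own free coefficients and so carries no information on β1. The generalized least squares estimate of β1 is therefore the raw difference in mean slopes, whatever x contains. Its standard error at given variance components is also unchanged.

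**Step 2: simulation.** Sixty data sets of n = 250 were generated with a true month-3 effect of .40. Assumed: a .3 SD covariate imbalance, with covariate and site related to both level and slope. Mean month-3 contrast:

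| Data | No covariates | Main effects as written | With covariate-by-time and site-by-time |
|---|---|---|---|
| Complete | .4397 | .4397 | .394 |
| 12% random loss | .447 | .448 | .401 |
| 12% loss dependent on the covariate, in opposite directions by arm | .391 | .421 | .402 |

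The difference between the first two columns within a data set was:

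- Complete data: at most 2e-15.
- Random loss: .006 on average in absolute size, at most .023 (0.36 standard errors).
- Adverse loss: .031 on average, at most .048 (0.76 standard errors).

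A second set of runs assumed a .25 SD imbalance, .30 SD of change per covariate SD and a true effect of 0. It gave mean contrasts of .071, .071 and −.003 in the same column order with complete data. The largest shifts from the main effects were .007 at 12% missing and .015 at 20%.

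**Step 3: size of what stays uncorrected.** The imbalance that just reaches p < .05 with 125 per arm is 1.96 × √(2/125) = .248 SD, about .25. No document gives the effect of a covariate on change, so I take .10 to .30 SD per SD:

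- .25 × .10 = .025 SD, and .025/.40 = 6%.
- .25 × .30 = .075 SD, and .075/.40 = 19%.

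A typical (one-SD) chance imbalance is √(2/125) = .126 SD. It leaves .126 × .10 = .013 to .126 × .30 = .038 SD.

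For scale, with correlation .50 the SD of change is √(1 + 1 − 2 × .50) = 1. A simple change contrast with 110 per arm then has standard error √(2/110) = .135. The .025 to .075 SD is thus about 0.19 to 0.56 standard errors.

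**Step 4: precision.** If the covariates explain 5 to 15% of the variance of change (assumed), interaction terms would cut the standard error by 1 − √.95 = 2.5% to 1 − √.85 = 8%.

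**The case against.** The strongest case against is that validity is not at stake. Condition is randomized, so the unadjusted change contrast is unbiased over randomizations, and its standard error already covers chance imbalance. The protocol itself expects few such differences. This stands, and it limits the point to lost conditional correction and lost precision.

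It can also be said that notes (5) and (6) are literally true of an equation for SF-12 at each time point, because the terms do adjust level. That is fair as a reading of the words. But the stated purpose is to handle confounders and imbalance in a model whose only test is on change.

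The exploratory analyses add three-way interactions with condition and time for illness category, participant characteristics and site. These could show that a covariate drives change, but they do not replace the primary estimate.

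Three stronger readings are tempting, and the protocol does not support them:

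- *The terms cannot change the estimate at all.* This holds only with complete data. Sample Size plans for 12% loss at post-treatment, and the H5 paragraph says all available data are used. The terms then have some effect, and they help support a missing-at-random analysis when dropout is related to covariates.
- *The primary estimate is biased by 19%.* That figure needs an imbalance at the significance threshold, which a given covariate reaches about 1 time in 20. It also needs an assumed .30 SD effect on change.
- *H1 and H2 are inconsistently adjusted.* Omitting the condition main effect in H2 is a disclosed choice made for power, with a stated fallback. It is not an error.

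**Conclusion.** The point holds in limited form. In H1 and the parallel H3 to H5 models, the stated adjustment for confounders, imbalanced covariates and site has no effect on the tested contrast with complete data. Under 12% random loss it has only a small effect, about .01 to .02 SD at most. The complete-data result is algebraic and rests on no assumed values. The size under loss depends on the dropout mechanism and was .031 on average in a deliberately adverse case.

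The practical cost is modest: .025 to .075 SD uncorrected in the illustrated imbalance, less for a typical one, and perhaps 2.5 to 8% in standard error. Both ranges rest on assumed covariate effects. The protocol prints this equation together with its stated purpose, so the mismatch is not a detail left open for a statistical analysis plan. It should be corrected.

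**What to change.** In H1 and its parallel models, add site-by-time and covariate-by-time terms for the prespecified covariates: age, race, gender, Charlson score and illness category. If time is later made categorical, use interactions with visit. Limit the interactions to this list. Extending them to variables picked by significance tests at randomization would make the primary contrast depend on data-driven selection.

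The cost is one line in the model statement and about ten parameters with 220 to 250 participants. Counting three sites (2), age (1), race in two groups as an assumption (1), gender (1), Charlson score (1) and five illness categories (4) gives 10. The downside is a few degrees of freedom.

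A baseline-adjusted month-3 model would be an alternative. If neither is adopted, state in notes (5) and (6) that the terms adjust level only, and do not describe the H1 treatment effect as adjusted for confounders or site.
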